2. STUDY OBJECTIVES

Primary objective

- To assess the clinical efficacy of azithromycin 300 mg i.v., used as a quorum-sensing blocker, when compared to placebo for preventing or delaying the occurrence of pneumonia in ventilated patients colonized with *Pseudomonas aeruginosa*

Secondary objectives

- To assess other clinical efficacy variables
- To compare safety profile in target population
- To demonstrate using both *in vivo* and *in vitro* parameters whether azithromycin can be used clinically as a quorum-sensing blocker against *P. aeruginosa*
- To determine whether *P. aeruginosa* can develop resistance to the quorum-sensing blocker effect of azithromycin
- To check whether prolonged treatment with azithromycin may induce resistance to any of 11 antipseudomonal antibiotics
- To verify whether emergence of resistance to other bacteriae may be elicited by assessing rate of infections in both study groups (azithromycin vs. placebo)

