- Adverse event profile (reported by subject, observed by investigator)
- Local tolerance (only if peripheral infusion site)
- Standard laboratory tests (see Appendix B)
- Blood gases
- Vital signs (blood pressure, heart rate, body temperature)

- 12-lead electrocardiogram (ECG)
- Emergence of non Pseudomonas infections

Statistical procedures

The primary analysis variable will be the occurrence of pneumonia, using Fischer's exact test. Other clinical and pharmacodynamic variables measured *in vivo* and *in vitro* will be analyzed by Fischer's test or chi-square for categorical variables (presence or absence of condition) whereas continuous variables will be compared using the t-test or the Mann-Whitney test, as considered best indicated. Appropriate graphs for key parameters as well as tables for all analyzed variables will be provided.

Descriptive analysis and listings will be produced for all safety variables (laboratory, adverse events, local tolerance).

Study duration and dates

The duration of this study is expected to be approximately 1 year, depending however heavily on number of assessable patients required (100 to 200) to achieve 10 pneumonia cases elicited by *P. aeruginosa*. Subject recruitment proposed is to start in November 2002 with study completion anticipated in Autumn 2003 to include a maximum of 240 cases for achieving 200 assessable patients.

STUDY SCHEDULE

ABBREVIATIONS AND DEFINITIONS

A-aD ₀₂	Alveolar-arterial P _{O2} difference (gradient)
aPTT	Activated partial thromboplastin time
ADR	Adverse drug reaction
AE	Adverse event
AIDS	Acquired immunodeficiency syndrome
ALT	Alanine aminotransferase (SGPT)
ANOVA	Analysis of variance
AP	Alkaline phosphatase
ARDS	Acute respiratory distress syndrome
AST	Aspartate aminotransferase (SGOT)
AUC	Area under the plasma concentration versus time curve over time periods: AUC ₀₋₂₄ , AUC _{0-∞}
BAL	Bronchial alveolar lavage
bpm	Beats per minute
BMI	Body Mass Index = Body weight (kg) / Height (m ²)
BP	Blood pressure
BW	Body weight
CFU	Colony forming unit (10 ^x /mL)
CAP	Community acquired pneumonia
Cl	Total clearance
C _{max}	Maximal plasma concentration
CPIS	Clinical Pulmonary Infection Score (see Appendix I)
CPK	Creatine phosphokinase
CRP	C-reactive protein
CRF	Case Report Form
C _{ss}	Plasma concentration at steady state
CV	Coefficient of variation
C _{xh}	Plasma concentration at end of infusion
DBP	Diastolic Blood Pressure
DR	Dose response
ECG	Electrocardiogram

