1.3 Background on azithromycin

Azithromycin, a macrolide with an azote in the lactone ring (azalide), has been selected to test this appealing mechanism of action for controlling *Pseudomonas aeruginosa* infections in humans, i.e. not by inhibiting its growth or causing death, but by reducing both its virulence and its capacity to colonize inert surfaces. The choice of azithromycin is based on substantial documentation in preclinical experiments and in infections with mutants having deficient genes, and on its excellent characteristics in terms of systemic tolerance, kinetic, metabolism (biliary excretion, low interaction potential, long biological half-life) and finally for its outstanding tissue distribution, both at interstitial and at intracellular level [33].

Azithromycin as an antibiotic acts by binding to the 50S ribosomal subunit of susceptible microorganisms, thereby interfering with their protein synthesis but without affecting their nucleic acid synthesis. It is active *in vitro* and in clinical infections against a wide spectrum of aerobic gram-positive agents (*Staphylococcus aureus*, *Streptococcus pneumoniae*), various staphylococci but not if methicillin-resistant and not against the majority of *Enterococcus faecalis* strains. Azithromycin shows cross-resistance to gram-positive strains resistant to erythromycin. It is not active against Enterobacteriaceae, *Pseudomonas* spp., or *Salmonella*. Despite its being a macrolide, azithromycin has however activity against some gram-negative agents such as *Haemophilus influenzae*, *Moraxella catarrhalis* and *Neisseria gonorrhoeae* and it is very active against some atypical microorganisms such as *Chlamydia pneumoniae* or *Legionella pneumophila* or against *Mycoplasma pneumoniae*. Minimum inhibitory concentrations for 90% of strains (MIC₉₀) are ≤ 0.5 $\mu\text{g/mL}$ for streptococci and 2 $\mu\text{g/mL}$ for other sensitive strains whereas for *Pseudomonas aeruginosa* it reaches ≥ 128 $\mu\text{g/mL}$, a massive difference [33].

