6.2 Prior and Concomitant Treatments - Antibiotherapy

Any treatment that are given in addition to the study treatment during the study is regarded as a concomitant treatment and must be documented on the appropriate pages of the CRF and in the subject's medical records, with dose adjustments as and if required. It is expected that a broad spectrum of concomitant treatments will need to be administered to treat the basic underlying disease or condition of these patients, to alleviate their symptoms, or to anticipate possible complications.

This may include antibiotics to treat infections, whenever possible selecting however an agent deprived of activity against *P. aeruginosa* or having demonstrated lack of activity against the specific strain isolated in that given patient. It is recommended to select an antibiotic to be used prior to or during the study for intercurrent infections from the table provided below to facilitate the choice of the investigators, to homogenize antibiotic treatment according to type of infections, and to limit interference with *P. aeruginosa* activity; one of these antibiotics should be given preferentially for empiric as well as for definitive therapy unless the clinical indication and/or resistance profile would justify another antibiotherapy.

Type of Infection	Recommended Antibiotics Deprived of Antipseumonal Activity
Vascular line infections	Methicillin, flucloxacillin, vancomycin, teicoplanin, synergid
Abdominal infections	Ceftriaxone +/- metronidazol
Urogenital infections	Ceftriaxone +/- metronidazol Amoxicillin + clavulanic acid +/- metronidazol
Pulmonary infections	Cetriaxone Amoxicillin + clavulanic acid
Central nervous system infections	Ceftriaxone, vancomycin
Skin infections	Penicillin, vancomycin, teicoplanin Amoxicillin + clavulanic acid

The following antibiotics listed in the table below have antipseudomonal activity and should be avoided for therapy unless the specific colonizing strain happens to be resistant or if mandatory during the study for clinical reasons. These same 11 antibiotics will be screened for MIC on bronchotracheal aspirate at study completion for assessing emergence of resistance.

11 Standard Antipseudomonal Antibiotics Not Recommended for Clinical Use* To Be Tested for MIC Pattern	
Carbenicillin	Ceftazidime
Piperacillin	Gentamycin
Piperacillin + tazobactam	Tobramycin
Imipenem	Amikacin
Ciprofloxacin	Meropenem
Cefepime	

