7.1.2. Pharmacodynamic data performed in local laboratory

A. Tracheal aspirates (on Aspirate 1)

- Collection daily
- Quantitative culture for *P. aeruginosa* (CFU/mL) on Day -1, 1, 3, 6, 9, 12, 15, 18 and last day (Day x, or Day n-1, or Day 20)
- Isolate *P. aeruginosa* strain daily and store at -70°C on skim milk and glycerol
- Emergence of resistance (MIC to *P. aeruginosa* in tracheal aspirate for 11 standard antipseudomonal antibiotics on Day -1 and on last day (Day x, or Day n-1, or Day 20) see list under Section 6.2)
- CFU for other strains from tracheal aspirates if indicated

B. BAL on Day x (or protected brush specimen (PBS) or bronchotracheal aspirate)

- Only for patients with suspected pneumonia for diagnosis
- CFU/mL
- Cellularity

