Adverse events reported during trial will be listed by treatment. Absolute and relative frequencies of subjects with adverse events (treatment emergent adverse events) will be tabulated by study part, by body system and by dose. Frequencies of subjects with severe and/or related adverse events will be summarized likewise. Local tolerance will be provided by time and by treatment and will be summarized with descriptive statistics for categorized variables by time and treatment.

Laboratory variables

Laboratory findings will be evaluated using a system of predefined changes and clinically significant abnormal values (provided by sponsor), taking into account the investigator's normal ranges. Listings of all variables will be provided by time and by treatment. Descriptive analysis will be presented by time and by treatment.

Physical examination

Listing of all variables will be provided by time and by treatment group. Descriptive analysis for raw data and for changes from baseline will be presented when appropriate.

Blood pressure and heart rate

Listing of all variables will be provided by time and by treatment. Descriptive analysis for raw data and for changes from baseline will be presented by time and by treatment.

ECG

Twelve-lead ECG will be recorded as described in Appendix I, at a speed of 25 mm/sec and calibrated at 10 mm/mV. If a QTc is prolonged (>450 ms or >60 ms vs. baseline), manual checking of QT and calculation of QTc with Bazett's formula will be performed by the investigator for safety purposes. When a patient will have completed treatment, all his ECGs will be transmitted to an experienced cardiologist for manual measurement as per Appendix J. The ECG parameters calculated manually by cardiologist will be used for statistical analysis.

Occurrence of infections

Information on distribution of infections to any bacterial strain will be collected and occurrence compared between study treatment.

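### The last secondary objective asks about resistance in bacteria other than P. aeruginosa, but the infection rate it relies on does not measure resistance and can mislead in either direction

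*Protocol*

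**What the plan says.** Section 2 and the synopsis name both the question and the method in one sentence: "To verify whether emergence of resistance to other bacteriae may be elicited by assessing rate of infections in both study groups".

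The data planned on bacteria other than *P. aeruginosa* are:

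- Section 7.1.1 and the synopsis: occurrence of infections with other strains, as a clinical efficacy variable.
- Section 7.1.4 and the synopsis: "Emergence of non Pseudomonas infections", as a safety variable.
- Section 7.1.2: "CFU for other strains from tracheal aspirates if indicated".
- Section 7.2.6: outcome at Day n+7, including infection and strain.
- Section 11.3: "Information on distribution of infections to any bacterial strain will be collected and occurrence compared between study treatment".

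Resistance is measured elsewhere. Section 6.2 lists 11 antipseudomonal antibiotics and says: "These same 11 antibiotics will be screened for MIC on bronchotracheal aspirate at study completion for assessing emergence of resistance". Sections 7.1.2 and 7.3 place this MIC testing on Day -1 and the last day, and only for *P. aeruginosa*. None of the 11 is a macrolide.

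Section 1.3 describes azithromycin as active "against a wide spectrum of aerobic gram-positive agents" and against some Gram-negative and atypical organisms, with cross-resistance in erythromycin-resistant Gram-positive strains. It also sets limits: "It is not active against Enterobacteriaceae", and it excludes methicillin-resistant staphylococci and most *E. faecalis*.

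**The concern.** The objective is about resistance, but the comparison attached to it is about how often patients become infected. The two can move independently, because the study drug is itself an antibiotic given for up to 20 days and acts on part of the flora being counted. A between-arm difference in infection rate, or its absence, therefore has no fixed meaning for resistance.

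For *P. aeruginosa* the protocol uses a direct measure, MIC at baseline and at the end. For other bacteria it uses a proxy only. A statistical analysis plan could add tables by organism, but it could not analyse susceptibility results that the protocol does not plan to collect. At stake is what the report may say about resistance outside *P. aeruginosa*.

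**Working it through.** The protocol gives no infection rate, resistance rate or power for this objective, so there is no figure to reproduce.

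**Step 1: question against data (non-*Pseudomonas* bacteria)**

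| Needed to answer | Planned? |
|---|---|
| Number of infections per arm | Yes (7.1.1, 7.1.4, 11.3) |
| Organism | Yes (7.2.6, 11.3) |
| Bacterial count | If indicated (7.1.2) |
| Susceptibility to a macrolide or any other drug | No |
| Stored isolates | Specified for *P. aeruginosa* only (7.1.2, Appendix D) |

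A change in the mix of species would be visible. A change from susceptible to resistant within one species, such as *S. aureus*, would not.

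**Step 2: masking (assumed rates)**

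Let *q* be the placebo infection rate, *r* the resistant share of it, *e* the fraction of susceptible infections prevented by azithromycin, and *m* the multiplier on resistant infections.

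Rate on azithromycin = q(1 − r)(1 − e) + q·r·m

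This equals *q* when m = 1 + e(1 − r)/r.

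| r | e = 0.3 | e = 0.5 | e = 0.7 |
|---|---|---|---|
| 0.20 | 2.2 | 3.0 | 3.8 |
| 1/3 | 1.6 | 2.0 | 2.4 |
| 0.50 | 1.3 | 1.5 | 1.7 |

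Over these ranges resistant infections could rise 1.3- to 3.8-fold with no change in the total.

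Example: q = 30%, r = 1/3, e = 0.5, m = 2. The azithromycin rate is 20% × 0.5 + 10% × 2 = 30%, the same as placebo. The protocol's 100 to 200 assessable patients give about 50 to 100 per arm. With Fisher's exact test at two-sided 0.10 (the level stated for the primary variable, assumed here), the chance of a significant excess on azithromycin is 3.7% with 100 per arm and 3.2% with 50. Those are the values when nothing happens at all.

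**Step 3: the opposite error (assumed rates)**

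Take the same 30%, but let the one third be species that azithromycin does not cover. Suppose they double by overgrowth and nothing is suppressed: 20% + 10% × 2 = 40% against 30%. The chance of a significant excess is 37.4% with 100 per arm and 21.5% with 50, although no organism has acquired resistance.

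**Step 4: why the resistant share of infections is no substitute**

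Suppose placebo has 14 susceptible and 6 resistant infections, a share of 6/20 = 30%. If azithromycin prevents half of the susceptible ones and resistant ones stay at 6, the share is 6/13 = 46%. If it prevents 80%, 2.8 susceptible infections remain and the share is 6/8.8 = 68%. The share rises with no increase in resistant infections.

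**Step 5: precision of a direct count**

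For patients with a resistant isolate at an assumed 6% against 12%, exact enumeration at two-sided 0.10 gives a chance of a significant excess on azithromycin of 34% with 100 per arm and 17% with 50. An observed 6/100 against 12/100 gives p = 0.22.

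**The case against.** The strongest defence is that the planned data are richer than one total. Strain and distribution of infections are collected, so a shift towards species listed in Section 1.3 as outside azithromycin's activity would show. That is correct, but it leaves resistance within a species unseen.

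Second, Section 6.2 refers to resistance profiles when choosing antibiotics, so local laboratories probably produce antibiograms. They may, but nothing provides for recording or comparing them for other bacteria.

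Third, this is the last of six secondary objectives in an exploratory Phase IIa trial, and neither the sample size nor the stopping rule depends on it. That is also correct and limits the weight of the point.

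A reader might go further and infer that azithromycin will push infection rates down, so that the trial would declare no emergence while resistant strains are being selected. The documents do not support that. Section 1.3 names many organisms the drug does not cover, so the direction depends on a mix of infections that the protocol does not describe. Patients in both arms may also receive other antibiotics under Section 6.2, so the added suppression is unknown. The protocol states no rule that an equal or lower rate means no emergence. Nor would a higher resistant share of infections show emergence, as step 4 makes clear.

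**Conclusion.** The objective is wrong as written: the comparison it names cannot show whether resistance emerges in other bacteria, and it can mislead in either direction. This conclusion rests on the protocol's text alone. The size does not: every infection rate, resistant share and degree of suppression used above is an assumption. The 1.3- to 3.8-fold range shows how much could be hidden; it does not predict what will happen.

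The effect is confined to one secondary objective and to what may be concluded from it. A direct count of resistant infections would address the question, but in a trial of this size it would be descriptive and imprecise.

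**What to change.** **Preferred.** In the synopsis and Section 2, reword the objective to: *compare the rate and species distribution of infections with other bacteria between arms*. State that no conclusion on resistance will be drawn from it. The cost is a change of wording.

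**Alternative, if the resistance objective is to be kept.**

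- For each non-*Pseudomonas* clinical isolate, record in the CRF the organism and, where the local laboratory reports it, macrolide susceptibility.
- Compare descriptively by arm the number of randomised patients with a macrolide-resistant isolate of a normally susceptible species.
- Report intrinsically resistant species separately.
- Use counts over all randomised patients, not the resistant share of infections.
- State that precision is low, citing the power in step 5.

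The cost is one or two CRF fields per infection. Macrolide results will be missing for some isolates, and without a baseline isolate, newly emerged resistance cannot be told from resistance carried at entry; the report should state both limits.

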3. STUDY DESIGN

This multicentre study follows a 2-parallel group, double blind, placebo controlled design, with daily i.v. administration of 300 mg azithromycin or saline (vehicle) over 1 hour. The duration of treatment for each mechanically ventilated patient will be for a maximum of 20 days (or earlier if extubation, if occurrence of pneumonia, or if exitus).

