PROOF-OF CONCEPT STUDY TO INVESTIGATE THE IMPACT OF AZITHROMYCIN ADMINISTERED I.V. VS. PLACEBO ON THE PREVENTION OF PNEUMONIA IN VENTILATED PATIENTS COLONIZED WITH *PSEUDOMONAS AERUGINOSA*

Coordinating Investigator

[name], Paris

Centre xx

Principal Investigator

Department

Hospital

Address

City, mail code

Country

List of Centres by Country

Each country centre list will include:

- National Coordinating Investigator
- Each site with:
 - Site number
 - Principal Investigator
 - Subinvestigators
 - Address
- Quintiles Study Monitor(s)

Phase IIa

Multinational and multicentric

Indication

Prevention of pneumonia in ventilated patients colonized with *Pseudomonas aeruginosa*

Objectives

Primary objective

- To assess the clinical efficacy of azithromycin 300 mg i.v., used as a quorum-sensing blocker, compared to placebo for preventing or delaying the occurrence of pneumonia in ventilated patients colonized with *Pseudomonas aeruginosa*

Secondary objectives

- To assess other clinical efficacy variables
- To compare safety profile in target population
- To demonstrate using both *in vivo* and *in vitro* parameters whether azithromycin can be used clinically as a quorum-sensing blocker against *P. aeruginosa*
- To determine whether *P. aeruginosa* can develop resistance to the quorum-sensing blocker effect of azithromycin

- To check whether prolonged treatment with azithromycin may induce resistance to any of 11 antipseudomonal antibiotics (list in Section 6.2.)
- To verify whether emergence of resistance to other bacteriae may be elicited by assessing rate of infections in both study groups (azithromycin vs. placebo)

Design

2-parallel groups, double blind, randomized, placebo controlled, multiple i.v. dose administered once daily

Population

- Intubated patients
- Age 18 to 75 years
- Males and non pregnant females
- Respiratory tract colonized by *Pseudomonas aeruginosa* as documented by tracheal aspirate

Sample size

- Recruit a total of 120 to 240 patients in order to achieve 100 to 200 assessable cases
- Stop recruitment when 10 *P. aeruginosa* pneumonia cases have been documented and confirmed by panel of experts under blinded conditions

Treatments

- 300 mg azithromycin as i.v. solution at 2 mg/mL or saline (placebo), infused daily over 1 hour, until extubation (Day n-1), occurrence of pneumonia (Day x), exitus, or for a maximum of 20 consecutive days (Day 20)

Clinical efficacy (clinical site)

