- Body temperature (tympanic or rectal) ~17:00
- Local tolerance (24 hours)
- Systemic tolerance (24 hours)

Day 3

On the morning of Day 3, prior to infusion of test drug, the following procedures will be performed:

- Adverse events from previous night
- Local tolerance
- Body temperature (tympanic or rectal) ~7:00
- Blood pressure, heart rate, respiration rate (~8:00)

- Blood (see Appendix B)
 - Hematological profile
 - Blood chemistry
 - WBC, CRP
- Specimen for blood culture (only if clinically indicated)
- Blood gases
- Oxygenation: PaO₂/ FI_{O2}
- CPIS (use results of lung X-ray of same day whenever possible)
- Clinical endpoints
- Tracheal aspirate 1 (transfer to local laboratory, for parameters see Section 7.1.2 above)
 - Quantification of *P. aeruginosa* (CFU/mL)
 - Isolation of *P. aeruginosa* strain (storage -70°C)

After these activities, the test drug will be infused over 1 hour, usually from 8 to 9 o'clock.

Post treatment activities will include:

- ECG, 1 to 4 hours post infusion start
- Tracheal aspirate 2 (for freezing and transfer to Geneva laboratory for investigation), collected ~6 hours post infusion start
- Blood pressure, heart rate, respiration rate (~6 hours post infusion start)
- BAL if required medically
- Lung X-ray whenever possible during the day
- Body temperature (tympanic or rectal) ~17:00
- Local tolerance (24 hours)
- Systemic tolerance (24 hours)

Subsequent study days in 3 day cycles (Day 4, 5 & 6; Day 7, 8 & 9; Day 10, 11 & 12; etc.)

This same treatment and sampling policy, using a 3-day cycle will be used until Day n which may correspond to Day 21 (24 hours after last treatment day i.e. after 20 days of treatment), or to extubation day because mechanical ventilation is medically not required any longer, or to exitus day (due to underlying disease complication, infection due to any strain type and site with or without sepsis, *P. aeruginosa* infections of non pulmonary location) and finally to Day x when *P. aeruginosa* pneumonia diagnosed.

The procedures to be performed daily or every third day are summarized in the Study Schedule (page 10) and as briefly reviewed below:

Day 4, 5, 7, 8, 10, 11, 13, 14, 16, 17, 19	Correspond to Day 2
Day 6, 9, 12, 15, 18	Correspond to Day 3
Day x (pneumonia, see below)	Corresponds to Day 3 with some additional parameters and study drug is terminated once diagnosis confirmed
Day n-1 or Day 20	Corresponds to Day 3, and is last day of test drug (with some additional parameters)

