7.2.4. Day x (Day of pneumonia)

The day when a diagnosis of established pneumonia or possible pneumonia is made, will be called Day x. Treatment against *P. aeruginosa* pneumonia will be initiated as soon as the diagnosis is confirmed or if this pathogen is considered as a highly likely cause of pneumonia. The Day x procedures will be implemented as completely as possible on that day (similar to Day n-1) and the remaining items will be performed the next day (Day n). The patient will not receive the test drug on the following morning and the patient will be discharged from the study on Day n with safety and physical examination.

In case of suspicion of pneumonia the necessary explorations will be performed in order to lead to a confirmed diagnosis based on the criteria for *P.aeruginosa* summarized in the table presented below:

Investigation	Documented Pneumonia Day x
BAL	$\geq 10^4$ CFU/mL
Or tracheobronchial aspirate	$\geq 10^5$ CFU/mL
Or protected brush specimen (PBS)	$\geq 10^3$ CFU/mL
CPIS* (see detailed score in App. I)	≥ 6

The diagnosis of pneumonia will be confirmed at later stage under double blind conditions by a panel of independent clinical experts prior to stopping the study to ensure that 10 documented cases of *P. aeruginosa* pneumonia have been included in the study for assessment. The data provided will be patient characteristics, symptoms, all CPIS parameters generated, CPIS overall scores, all X-rays collected and results of BAL (or tracheobronchial aspirate or protected brush). Efforts will be made to achieve a total of 10 pneumonia cases in patients who do not receive concomitant therapy with an antibiotic with activity against the isolated *P. aeruginosa* strain, providing however the overall constraint for a maximum of 240 patients entered will not be trespassed.

Post treatment activities will include:

- Tracheal aspirate 2 (for freezing and transfer to Geneva laboratory for investigation), collected early afternoon (usually 6 hours [if Day x] or 30 hours [if Day n and if applicable] after last test drug administration) if patient still intubated and even if antipseudomonal antibiotherapy has been meanwhile initiated
- ECG, 1 to 4 hours late morning Day x
- Blood pressure, heart rate, respiration rate (early afternoon Day x or Day n)
- Lung X-ray whenever possible that day

- Body temperature (tympanic or rectal) ~17:00
- Local tolerance (up to 24 hours)
- Systemic tolerance (up to 24 hours)

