11.3 Statistical Methods

The primary analysis variable will be the occurrence of pneumonia in both treatment groups (azithromycin vs. placebo), using Fischer's exact test (two-sided, $p=0.10$) and based on 10% in placebo group. Other clinical variables and all pharmacodynamic variables measured *in vivo* and *in vitro* will be analyzed by Fischer's test, by paired t-test, by Mann Whitney test, or by ANOVA using adequate models, as considered best indicated. The list of all clinical and pharmacodynamic variables considered is provided in Section 7.1.1.

Clinical and Pharmacodynamic Variables

Appropriate graphs for key parameters as well as tables for all analyzed variables will be provided. A subpopulation analysis will be attempted for the primary variable and for selected secondary clinical and pharmacodynamic variables, taking into account if patients are considered as being at risk at study entry:

- Treatment with steroid or antibiotherapy
- Lung damage or transplant
- >72 hours of hospitalization prior to intubation

The variables will be analyzed for all patients and for patients without antibiotic therapy or with antibiotics deprived of activity against the colonizing *P. aeruginosa* strain (Subgroup 1) and for patients treated with antibiotics with *P. aeruginosa* activity (Subgroup 2). If no difference between response to study drug treatment (azithromycin vs. placebo) is seen when considering Subgroup 1 and Subgroup 2, all patients will be combined. If feasible, comparisons of response taking into consideration risk factors (e.g. for subgroups with 0, 1, ≥ 2 risk factors) will be attempted. A detailed statistical plan will be prepared by the responsible statistician prior to decoding the study.

Clinical endpoints and outcome variables as well as pharmacodynamic variables may be used as categorical event (yes, no), as raw data (for days, concentration, score for CPIS and APACHE II score, ventilation parameters, CFU, ...), as log transformed data, as differences to baseline, or as % change of baseline. All measured and calculated variables will be presented as listings by time and by treatment and, if indicated, as difference to baseline and as % change of baseline.

Graphs illustrating time effect will be provided.

Safety parameters

Adverse events

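### The protocol contradicts itself on whether pneumonia from another organism ends treatment and participation, and the primary-test sentences do not name *P. aeruginosa*

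*Protocol*

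**What the plan says.** **What ends treatment and participation**

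- Protocol Section 3 limits treatment to 20 days, "or earlier if extubation, if occurrence of pneumonia, or if exitus". No organism is named.
- The synopsis (Treatments) ends dosing at "occurrence of pneumonia (Day x), exitus, or for a maximum of 20 consecutive days (Day 20". It adds the Day x label but names no organism.
- Section 7.2.4 opens: "The day when a diagnosis of established pneumonia or possible pneumonia is made, will be called Day x". The consequence is: "The patient will not receive the test drug on the following morning and the patient will be discharged from the study on Day n".
- Section 7.2.3 lists what Day n may correspond to, "finally to Day x when *P. aeruginosa* pneumonia diagnosed".
- Section 6.2 takes a patient out of the study once *P. aeruginosa* pneumonia has been diagnosed by quantitative culture, and for no other pneumonia. On other infections it says: "It is recommended to select an antibiotic to be used prior to or during the study for intercurrent infections from the table provided below". That table has a row for pulmonary infections.
- Section 7.2.5 lists extubation, death and Day 20 as the last treatment day. Pneumonia is not in its list.

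**What the primary event is**

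- The synopsis (Clinical efficacy) and Section 7.1.1 label *P. aeruginosa* pneumonia as the primary variable. Section 4.1 stops recruitment at 10 panel-confirmed cases of it.
- Section 11.3 says: "The primary analysis variable will be the occurrence of pneumonia in both treatment groups (azithromycin vs. placebo"). The synopsis paragraph on statistics and Section 11.5 also speak of pneumonia without an organism, as does the wording of the primary objective in Section 2.

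**Why the organism matters**

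- Section 1.3 says of azithromycin: "It is active *in vitro* and in clinical infections against a wide spectrum of aerobic gram-positive agents", naming *S. aureus* and *S. pneumoniae*. It adds *H. influenzae* among the gram-negatives.

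**The concern.** Take a patient with a staphylococcal pneumonia on Day 6. A site following Section 3 and the opening of Section 7.2.4 stops study drug and discharges the patient. A site following Sections 6.2 and 7.2.3 treats the infection and carries on, up to Day 20. These are site instructions, so a later analysis plan cannot undo what sites have already done.

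The trial is meant to show quorum-sensing blockade as distinct from ordinary antibacterial action (Section 1.4). Other-organism pneumonia is where the two could be confused, because the drug is active against several organisms that can cause it. Two consequences have to be kept apart:

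1. If such a pneumonia counts as the primary event, an antibacterial effect could pass for a quorum-sensing effect.
2. If it does not count but ends participation, it competes with the primary event, and patients leave before they can have one.

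**Working it through.** **Plan's own figure.** Section 11.5 assumes 10% pneumonia on placebo and 10 cases in total. With risk ratio RR, n per arm = 10 / (0.10 + 0.10 × RR).

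- RR = 1: 10/0.20 = 50 per arm, 100 in total.
- RR = 0: 10/0.10 = 100 per arm, 200 in total.

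Both match the stated range of 100 to 200 assessable patients.

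**Inputs from the protocol.** Two-sided Fisher exact test at 0.10 (Section 11.3), equal allocation (Section 5.3), 20 days of treatment, 10% placebo rate.

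**Assumptions (no figure in the protocol).** No effect on *P. aeruginosa* pneumonia, so 10% in both arms. Placebo risk q of other-organism pneumonia is 5%, 10% or 20% over 20 days. The azithromycin hazard ratio (HR) on it is 0.5 or 0.25. Hazards are constant.

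**Case 1: any pneumonia is the primary event.** Placebo rate = 1 − 0.90 × (1 − q). Azithromycin rate = 1 − 0.90 × (1 − q)^HR. For q = 10% and HR = 0.5: 1 − 0.90 × 0.90 = 19.0%, against 1 − 0.90 × 0.949 = 14.6%. The chance of p≤0.10 sums the binomial probabilities of all tables that reach it.

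| q | HR | Placebo | Azithromycin | Chance of p≤0.10, 100 per arm | 50 per arm |
|---|---|---|---|---|---|
| 5% | 0.5 | 14.5% | 12.3% | 0.10 | 0.07 |
| 5% | 0.25 | 14.5% | 11.1% | 0.13 | 0.08 |
| 10% | 0.5 | 19.0% | 14.6% | 0.16 | 0.10 |
| 10% | 0.25 | 19.0% | 12.3% | 0.30 | 0.16 |
| 20% | 0.5 | 28.0% | 19.5% | 0.35 | 0.19 |
| 20% | 0.25 | 28.0% | 14.9% | 0.68 | 0.39 |

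When the arms do not differ, the chance is 0.06 to 0.07 at 100 per arm and 0.05 to 0.06 at 50. The 50-per-arm column is there because, with no effect, Section 11.5's own arithmetic reaches 10 *P. aeruginosa* cases at about that size.

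Counting other organisms also hurts if azithromycin does nothing to them. For a halved *P. aeruginosa* rate (10% vs 5%, 100 per arm), power falls from 0.28 to 0.21, 0.17 and 0.13 at q = 5%, 10% and 20%.

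**Case 2: only *P. aeruginosa* pneumonia counts, but any pneumonia ends participation.** Let H = −ln(0.90) = 0.105. Let G = −ln(1 − q) on placebo and HR times that on azithromycin. The observed *P. aeruginosa* risk is H/(H + G) × [1 − exp(−(H + G))]. For q = 10% and HR = 0.5: placebo 0.5 × 0.19 = 9.50%, azithromycin (0.1054/0.1580) × 0.1462 = 9.75%, ratio 1.026.

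| q | Ratio, HR 0.5 | Ratio, HR 0.25 |
|---|---|---|
| 5% | 1.013 | 1.019 |
| 10% | 1.026 | 1.039 |
| 20% | 1.055 | 1.084 |

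In events per 75 placebo patients, q = 5% gives 75 × (0.1000 − 0.0975) ≈ 0.2 lost, and q = 15% gives 75 × (0.1000 − 0.0924) ≈ 0.6.

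**The case against.** **Day x is specific to *P. aeruginosa* in context.** The diagnostic table in Section 7.2.4 gives criteria for that organism. Appendix I explains possible pneumonia as a score of 6 or more for *P. aeruginosa* with counts below the cut-off, and the synopsis ties its stop to Day x. This narrows the conflict without removing it. Section 3 has no Day x label. The second sentence of Section 7.2.4 makes antipseudomonal treatment depend on that organism being confirmed or highly likely, which leaves room for a Day x with another cause.

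**The primary variable is named elsewhere.** Section 11.3 refers to the list in Section 7.1.1, and the count of 10 cases uses *P. aeruginosa* pneumonia. This stands. A reader might infer that the trial has two rival primary endpoints; the documents point to one, loosely worded where the test is fixed.

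**Azithromycin need not change other-organism pneumonia.** A reader might infer from Section 1.3 that its activity makes this event differ by arm. The documents do not show that. They give no rates, exclude methicillin-resistant staphylococci and Enterobacteriaceae from its spectrum, and expect concomitant antibiotics. Only the possibility of a difference is supported.

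**Early exit does little damage.** A reader might infer that lost placebo events could overturn a borderline result. The expected loss is a fraction of one event, and recruitment continues to 10 cases unless the 240-patient cap intervenes, so a lost event would normally lengthen recruitment. The bias also runs against azithromycin and cannot create a false positive. This stands.

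**Other infections are already captured.** Sections 7.1.1 and 11.3 compare them by arm, and Section 7.2.6 records pneumonia and strain at Day n+7. That covers part of the reporting. It does not settle what sites do with study drug, and a patient who leaves on Day 6 is followed for only about one further week.

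**Conclusion.** The contradiction on what ends treatment and participation is firm and operational, and should be resolved. The gap on the primary event is softer: *P. aeruginosa* pneumonia is the likely intent, but the sentences that fix the test should say so.

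The size depends on which reading is applied. If any pneumonia were counted, a false signal for quorum-sensing blockade could arise in about 10% to 68% of trials at 100 per arm (7% to 39% at 50 per arm). If other-organism pneumonia only ended participation, the apparent risk ratio would be about 1.01 to 1.08, against azithromycin. Both ranges rest on an assumed placebo other-organism risk of 5% to 20%, hazard ratios of 0.5 and 0.25, and no effect on *P. aeruginosa*. The protocol supplies none of these, so the figures illustrate what could happen and do not forecast it.

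**What to change.** 1. Reconcile the synopsis (Treatments) and Sections 3, 6.2, 7.2.3, 7.2.4 and 7.2.5 so that one stated rule on study drug applies after pneumonia from another organism. Which rule is for the sponsor to decide.
2. Whatever that rule is, state that such a pneumonia does not end observation for *P. aeruginosa* pneumonia within the planned follow-up.
3. In Sections 11.3 and 11.5 and the synopsis statistics, name panel-confirmed *P. aeruginosa* pneumonia as the primary analysis variable.
4. Report other-organism pneumonia by arm as a line within the infection comparison that Section 11.3 already plans.

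The cost is amendment wording and continued data collection for a few patients. No new procedure is needed, because diagnostic sampling is already done when pneumonia is suspected.
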